8.4.2 CXCL9 assay

The time points for assessment of CXCL9 are indicated in the assessment schedule Table 5a for patient of weight ≥ 30 kg and in Table 5b for patients of weight < 30 kg. Some assessments are not performed in patients of weight < 15 kg and these are indicated with an (*) in the assessment schedule.

CXCL9 in serum will be measured locally with a validated assay. A device to perform the CXCL9 measurements will be provided to the sites by Sobi AG.

CXCL9 is the primary predictive biomarker used for treatment decision in combination to other clinical laboratory assessments for both primary and secondary graft failure. The exact CXCL9 threshold for treatment initiation and instructions for use of the technology will be provided in the CXCL9 assay laboratory manual.

- Pre-HSCT - Patients presenting CXCL9 levels 10 times above the upper limit of the 95% CI of the normal range (please refer to CXCL9 assay laboratory manual) within 24 hours prior to HSCT are not eligible.
- Post-HSCT - Starting from day 1 during the monitoring and extended monitoring, CXCL9 will be measured to assess eligibility to treatment.

Leftover of the CXCL9 sample will be shipped to Sobi AG (Switzerland) for further exploratory analyses as defined in the exploratory endpoints section 7.6. Further details on the sample to be collected, volume and processing will be provided in a laboratory manual for the CXCL9 assay.

8.4.3 Pharmacokinetic, pharmacodynamics, immunogenicity and other exploratory assessments

PK, PD and immunogenicity will be performed during the study at the time points as detailed in the assessments schedule (Table 5a, Table 6a and Table 7a for patient of weight ≥ 30 kg and in Table 5b, Table 6b and Table 7b for patients of weight < 30 kg). Some assessments are not performed in patients of weight < 15 kg and these are indicated with an (*) in the assessment schedule.

Details of which parameters will be assessed are reported in section 7.3 (immunogenicity), section 7.4 (pharmacokinetics), section 7.5 (pharmacodynamics) and section 7.6 (exploratory endpoints).

Details on sample preparation and handling will be described in a laboratory manual.

9 SAFETY DEFINITIONS AND REPORTING REQUIREMENTS

9.1 Adverse Events

9.1.1 Definition of Adverse Events

An Adverse Event (AE) is any adverse change i.e. any unfavorable and unintended sign, including an abnormal laboratory finding, symptom or disease that occurs in a subject during the course of the study (after signing of the informed consent), whether or not considered by the investigator as related to study treatment.

A treatment-emergent AE is any AE temporally associated with the use of study treatment whether or not considered by the investigator as related to the study treatment.

AEs include:

- Exacerbation of a pre-existing disease.
- Increase in frequency or intensity of a pre-existing episodic disease or medical condition.
- Disease or medical condition detected or diagnosed during the course of the study even though it may have been present prior to the start of the study.
- Continuous persistent disease or symptoms present at study start that worsen following the start of the study.
- Abnormal assessments, e.g., change on physical examination, ECG findings, if they represent a clinically significant finding that was not present at study start or worsened during the course of the study.
- Laboratory test abnormalities if they represent a clinically significant finding, symptomatic or not, which was not present at study start or worsened during the course of the study or led to dose reduction, interruption or permanent discontinuation of study treatment.

AEs diagnosis versus signs/symptoms

For any AE, a diagnosis should be recorded rather than individual signs and symptoms. However, if at the time of AE reporting, a diagnosis is not available, each individual sign/symptom should be recorded. If a diagnosis is subsequently established, all previously reported AEs based on signs and symptoms should be removed and replaced by one AE report based on the single diagnosis, with a starting date that corresponds to the starting date of the first symptom of the eventual diagnosis.

Persistent and recurrent AEs

A persistent AE is such an event that extends without resolution over period of time. Such events should only be recorded once. A recurrent AE is such an event that recurs at intervals with resolution after individual recurrences. Each recurrence of an AE should be recorded as a separate event.

AEs should be recorded in the appropriate section of the eCRF.

9.1.2 Intensity of Adverse Events

The intensity of clinical AEs is graded on a three-point scale (mild, moderate and severe).

If the intensity of an AE worsens during study treatment administration, only the worst intensity should be reported on the AE page. If the AE lessens in intensity, no change in the severity is required.

For AEs not listed in the World Health Organization (WHO) toxicity scale, the three categories of intensity are defined as follows:

- Mild: The event may be noticeable to the subject. It does not influence daily activities, and usually does not require intervention.
- Moderate: The event may make the subject uncomfortable. Performance of daily activities may be influenced, and intervention may be needed.

- Severe: The event may cause noticeable discomfort, and usually interferes with daily activities. The subject may not be able to continue in the study, and treatment or intervention is usually needed.

A mild, moderate, or severe AE may or may not be serious (see section 9.2.1 for definition of SAE). Medical judgment should be used on a case-by-case basis.

Seriousness, rather than severity assessment, determines the regulatory reporting obligations.

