9.1.4 Reporting of adverse event

For both treated and untreated patients, AEs must be collected until EoS visit. All AEs occurring after study start (i.e., signing of informed consent) must be recorded in the AE pages of the eCRF.

All AEs should be followed until the event has resolved. AEs still ongoing at EoS visit should be followed until they are no longer considered clinically relevant for both treated and untreated patients.

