12.5.3 Safety Data

Safety data will be listed and summarized using descriptive statistics.

AEs will be coded and tabulated by body system, and by individual events within each body system. AEs will also be tabulated by severity and relationship to the study medication. Summaries will also be produced of SAEs and AEs leading to withdrawal of treatment.

For each clinical laboratory test, individual patient values will be listed and summarized, and change from pre-treatment baseline values calculated and summarized. Any values outside the standard reference range will be flagged. Summaries of marked abnormalities and shift tables or boxplots will be tabulated for each laboratory test.

In addition, other exploratory analyses of safety data, including summaries for different subsets of patients, may be conducted.

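### For clinical AEs already ongoing at first dose, a single record holding only the worst intensity cannot show whether the event worsened on emapalumab or was severe beforehand and improved

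*Combined protocol and SAP*

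**What the plan says.** Section 9.1.4 starts AE collection well before treatment: "All AEs occurring after study start (i.e., signing of informed consent) must be recorded in the AE pages of the eCRF". Section 9.1.1 treats an event that continues without resolving as one entry: "Such events should only be recorded once". Only an event that resolves and then returns is given a separate entry.

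Section 9.1.2 fixes the grade on that entry. For worsening: "If the intensity of an AE worsens during study treatment administration, only the worst intensity should be reported on the AE page". For improvement: "If the AE lessens in intensity, no change in the severity is required". Nothing in Section 9.1 asks for the grade at first dose, the date of worsening, or a new record when an event worsens. The only explicit rule on start dates, for symptoms later replaced by a diagnosis, points backwards: "with a starting date that corresponds to the starting date of the first symptom of the eventual diagnosis".

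Treatment emergence is defined in Section 9.1.1 as follows: "A treatment-emergent AE is any AE temporally associated with the use of study treatment", regardless of causality. There is no reference to the first infusion, no time window and no criterion for worsening from a pre-dose state. The list of what counts as an AE does include worsening, for example "Continuous persistent disease or symptoms present at study start that worsen following the start of the study", but no item takes first dose as its reference point.

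Section 12.5.3 plans tables by body system and event, and adds: "AEs will also be tabulated by severity and relationship to the study medication". Section 12.5 presents data by dose regimen, for all emapalumab patients and for untreated patients. Neither section states a split between pre-dose and on-treatment AEs.

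**The concern.** Patients reach first dose after conditioning and transplant, so clinical toxicities may already be on the AE page. The recording rules then keep one grade (the worst) and, by implication, one start date (the first). What a safety reviewer needs to know about an event already present at first dose is whether it got worse on drug. That information is not collected.

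The loss occurs at data capture. A later analysis plan can tighten the definition of treatment emergence, but it cannot recover a grade or a date that no one recorded. Causality is affected too: one record carries one relatedness judgement, and the first item of guidance in Section 9.1.3 is the timing of onset relative to the start of study drug. A pre-dose onset date leans towards unrelated, even for an event that worsened on treatment.

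Safety is a supporting objective, and safety data go to the Dose Decision Committee (Section 3.6.2) and into the benefit-risk assessment before each dose transition (Section 12.2). Severity tables by dose regimen should therefore mean what they appear to mean.

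**Working it through.** The plan gives no figure to reproduce. The check is day arithmetic plus a test of whether the prescribed record can tell two opposite histories apart.

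**Length of the pre-dose recording period.** Inputs: screening runs from Day -21 to Day -8 (Section 3.4.1); first dose for primary graft failure falls between Day 1 and Day 42, and for secondary graft failure at up to Day 98 (Section 3.1). Consent is taken to fall in the screening window, and visit windows are ignored.

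- Shortest: 8 + 1 = 9 days.
- Longest, primary graft failure: 21 + 42 = 63 days.
- Longest, secondary graft failure: 21 + 98 = 119 days.

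In every case the period includes the transplant.

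**Two histories of one persistent clinical AE (say, mucositis) with onset before first dose.**

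| | Before first dose | On treatment | Rule applied | AE-page entry |
|---|---|---|---|---|
| A | severe | mild | no change on improvement | one record, pre-dose start, severe |
| B | mild | severe | worst intensity only | one record, pre-dose start, severe |

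The entries are identical. The pre-dose start date in row B is an inference: the text does not say outright that a worsened AE keeps its original date, but it allows only one record and has no rule to re-date it.

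**Effect under each way of applying the treatment-emergent definition.**

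- By start date: neither A nor B counts. A is classified correctly, and the worsening in B is missed.
- By being ongoing during treatment: both count as severe. B is classified correctly, and A is wrongly shown as a severe event on drug.

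Each reading gets one history right and the other wrong. No definition applied to these fields gets both right.

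**Size of one error.** With 4 evaluable patients in a cohort, 1/4 = 25 percentage points. With 10 at the selected dose, 1/10 = 10 points. These are upper figures for a dose-regimen column, because treated patients also include non-evaluable and secondary graft failure patients. If a cohort treated as many patients for secondary as for primary graft failure, as Section 12.1 contemplates, the combined column would hold 4 + 4 = 8, and one error would be 1/8 = 12.5 points.

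**The case against.** The strongest reply is that the events that matter most here are protected elsewhere. Most of that stands.

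- **Infections.** A reader might infer that infections present before dosing are the main casualty. The documents do not support this. Section 3.4.3 bars treatment when a clinically active infection is present at initiation, whether or not it is being treated; clinical manifestations of the listed pathogens and GvHD are also bars. Infections that become clinically active later have their own post-dose onset. What remains is mainly viral positivity without clinical infection, for which Table 6a schedules testing at dose 1, with repeats at doses 5 and 10 in positive patients.
- **Cytopenias.** Hematology with differential is scheduled at dose 1 in Tables 6a and 6b, and Section 12.5.3 requires change from a pre-treatment baseline, with shift tables or boxplots. The pre-dose severity of a laboratory abnormality is therefore kept.
- **Serious worsening.** Section 9.2.2 requires an SAE form and follow-up reports, which may document the course of the event. This helps only for serious events.
- **Deferral to the SAP.** Section 12.5 leaves full analysis detail to the SAP. No separate SAP section or eCRF completion instructions were in the text available, so a sharper definition or a pre-dose tabulation may exist there. It would not restore a grade or date that the AE page never held.
- **Only one reading would be applied.** True: the two errors are alternatives. But whichever reading is chosen, one type of error remains.

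The reply narrows the point to clinical, non-laboratory AEs that do not bar treatment, chiefly non-serious ones. It does not remove it.

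**Conclusion.** The point holds in this limited form. For a non-laboratory AE ongoing at first dose, the AE page as specified cannot distinguish worsening on emapalumab from pre-dose severity that later improved, and severity tables by dose regimen can be wrong in either direction.

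The documents do not say how often this would happen; that some transplant toxicities will be ongoing at first dose is plausible from the timing but is an assumption. The 25- and 10-point shifts illustrate the effect of one error at evaluable counts of 4 and 10 and are not estimates of bias.

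A reader might also infer that dose selection or stopping would be driven by the error. The documents do not show that. Section 12.2 bases cohort decisions on IFNγ, CXCL9 and PK/PD data with an overall benefit-risk review, and bases stopping for futility or success on graft failure counts. Sections 11.1.2 and 11.2 rely on life-threatening reactions, related serious events and deaths, and clinical or committee judgement. None uses a severe treatment-emergent rate. All analyses are declared exploratory. This is a cheap improvement to safety reporting, not a threat to the trial's main conclusions.

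**What to change.** - **Section 9.1.2 and eCRF instructions.** For an AE ongoing at first dose, any increase in intensity after that dose opens a new record with its own onset date, intensity and causality. Alternatively, keep one record and add the intensity at first dose and the date of worsening.
- **Section 9.1.1.** Define a treatment-emergent AE as one with onset, or an increase in intensity, on or after the first infusion and up to the EoS visit. This matches the existing end of AE collection in Section 9.1.4.
- **Section 12.5.3 and SAP.** Tabulate the pre-dose AEs of treated patients separately from their treatment-emergent AEs.

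The cost is a few sentences of protocol and SAP text, plus either slightly more AE lines for sites or a small addition to the AE page. No additional patient assessments are needed.

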9.1.3 Relationship to study treatment

Each AE must be assessed by the investigator as to whether or not there is a reasonable possibility of causal relationship to the study treatment and reported as either related or unrelated. The determination of the likelihood that the study drug caused the AE will be provided by an investigator who is a qualified physician.

Investigators should use their knowledge of the patient, the circumstances surrounding the event, and an evaluation of any potential alternative causes to determine whether or not an adverse event is considered to be related to the study drug. The following guidance should be taken into consideration:

- Temporal relationship of event onset to the initiation of study drug.
- Course of the event, considering especially the effects of dose reduction, discontinuation of study drug, or reintroduction of study drug (as applicable).
- Known association of the event with the study drug or with similar treatments.
- Known association of the event with the disease under study.

9.1.4 Reporting of adverse event

For both treated and untreated patients, AEs must be collected until EoS visit. All AEs occurring after study start (i.e., signing of informed consent) must be recorded in the AE pages of the eCRF.

All AEs should be followed until the event has resolved. AEs still ongoing at EoS visit should be followed until they are no longer considered clinically relevant for both treated and untreated patients.

9.2 Serious adverse event (SAEs)

9.2.1 Definitions of SAEs

A serious adverse event is any AE that meets any of the following criteria (as per ICH guidelines):

- Is fatal.
- Is life-threatening (note: the term "life-threatening" refers to an event in which the patient was at immediate risk of death at the time of the event; it does not refer to an event which could hypothetically have caused a death had it been more severe).
- Requires in-patient hospitalization or prolongs an existing hospitalization.
- Results in persistent or significant disability/incapacity.
- Is a congenital anomaly/birth defect.
- Medically significant: refers to important medical events that may not immediately result in death, be life-threatening, or require hospitalization but may be considered to be SAEs when, based upon appropriate medical judgment, they may jeopardize the subject, and may require medical or surgical intervention to prevent one of the outcomes listed in the definitions above.

The following reasons for hospitalization are exempted from being reported:

- Hospitalization for social and/or convenience reasons.
- Hospitalization for pre-planned (i.e., planned prior to signing informed consent) surgery or standard monitoring of a pre-existing disease or medical condition that did not worsen.

However, complications that occur during hospitalization are AEs or SAEs (for example if a complication prolongs hospitalization or is medically significant as defined above).

9.2.2 Reporting of SAEs

For both treated and untreated patients, all SAEs occurring after study start (i.e., signing of informed consent) must be recorded in the AE pages of the eCRF. Collection of SAEs is required until EoS visit for both treated and untreated patients.

For emapalumab treated patients, new SAEs occurring after the EoS (during the 3 years survival check) must be reported to the Sponsor within 24 hours of the investigator's knowledge of the event, **only** if considered causally related to previous exposure to the study treatment by the investigator.

SAEs still ongoing at EoS visit must be followed up until resolution or stabilization, or until the event outcome is provided, e.g., death.

Reporting procedures

All SAEs must be reported by the investigator to the Sponsor within 24 hours of the investigator's first knowledge of the event.

All SAEs must be recorded on an SAE form, irrespective of the study treatment received by the subject, and whether or not this event is considered by the investigator to be related to study treatment.

The SAE forms must be emailed to the Sobi Global Pharmacovigilance & Patient Safety department (contact details are provided on the SAE form). The investigator must complete the SAE form in English and must assess the causal relationship of the event to study treatment.

Follow-up information about a previously reported SAE must also be reported within 24 hours of receiving it. The Sponsor may contact the investigator to obtain further information.

If the subject is hospitalized in a hospital other than the study site, it is the investigator's responsibility to contact this hospital to obtain all SAE relevant information and documentation.

The reference safety document to assess expectedness of a suspect serious adverse reaction and reported by the sponsor to Health Authorities, Independent Ethic Committees (IECs)/Institutional Review Boards (IRBs) and investigators is the reference safety information section of the current version of the IB.

9.3 Pregnancy

Emapalumab treatment must be permanently discontinued in case of pregnancy. The investigator must counsel the subject and discuss the risks of continuing pregnancy and the possible effects on the fetus.

In case of pregnancy, emapalumab treated patients will move to follow-up period. Non-emapalumab treated patients will be withdrawn after performing the EoS/withdrawal visit.

9.3.1 Reporting of pregnancy

Irrespective of whether emapalumab treatment was received or not, any pregnancy up to EoS visit must be reported.

All pregnancies should be reported using the Sobi Pregnancy Notification Form, which must be sent to the Sponsor (email contact details provided on the Pregnancy Notification Form) within 24 hours of the investigator's knowledge of the pregnancy.

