3.4.5 Follow-Up Period

Assessments to be performed during the follow-up period are detailed in the Schedule of Assessments (Table 7a and Table 7b). The follow-up period will last 3 years from the HSCT date for both patients who received and those who did not receive emapalumab, as detailed below.

Follow-up period: emapalumab treated patients

All emapalumab treated patients will enter the follow-up period:

- (i) Upon completion of treatment or engraftment, whichever comes first
- (ii) In case of premature treatment discontinuation for any reason

The follow-up period for patients who received emapalumab will consist of 6 visits: at 1 week \pm 2 days, 2 weeks \pm 2 days, 4 weeks \pm 2 days, 8 weeks \pm 1 week, 12 weeks \pm 1 week and 24 weeks \pm 2 weeks after last study drug administration (EoS visit) and 3 phone calls for survival observation at 1, 2 and 3 years after HSCT.

During the survival calls defined concomitant medications/procedures (i.e. any HSCT, blood product transfusion, stem cell boost, DLI or hematopoietic agents) and occurrence of GvHD since previous visit/call should be recorded.

The first follow-up visit will be 1 week \pm 2 days after last study drug administration or 1 week after EoT (in case of treatment discontinuation or engraftment before the last dosing day).

Follow-up period: non-emapalumab treated patients

In case treatment with emapalumab has not been initiated, patients will undergo an EoS visit (within 1 week from the last day in the monitoring periods) and enter the phone calls follow-up.

A patient can enter follow-up in the following occasions:

- (i) At the end of the monitoring (Day 42) or extended monitoring (Day 98).
- (ii) If they require a second HSCT anytime during the monitoring periods.
- (iii) If any prohibited medication is taken during the monitoring periods.
- (iv) In case of re-occurrence of malignant disease, GvHD diagnosis, uncontrolled infection or clinical manifestations of infections representing exclusion criteria at time of eligibility to treatment.

The follow-up period for non-emapalumab treated patients will consist of 4 phone calls at 6 months, 1, 2 and 3 years after HSCT. During the survival calls defined concomitant medications/procedures (i.e. any HSCT, blood product transfusion, stem cell boost, DLI or hematopoietic agents) and occurrence of GvHD since previous visit/call should be recorded.

End of Study Visit

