Assessments to be performed during the EoS visit are detailed in the Schedule of Assessments (Table 7a and Table 7b).

- For emapalumab treated patients, the EoS visit correspond to the last follow-up visit (Follow-up visit 6) at week 24 \pm 2 days from last study drug administration.
- Non-emapalumab treated patients will require to attend the EoS visit within 1 week from the last day in the monitoring periods.

Table 2 Transition between periods in case of ANC < 500 cells/ μ L during the monitoring period

Monitoring	Treatment	Follow-up For emapalumab treated patients	Follow-up For non-emapalumab treated patients
CXCL9 above threshold + ANC <500 cells/ μ L 	Enter treatment period		Perform EoS visit and enter phone-calls follow-up period:
CXCL9 below threshold + ANC <500 cells/ μ L  Continue monitoring ✓ Unless a second HSCT is required ✓ As soon as ANC \geq 500, transition to extended monitoring Table 3		Enter follow-up period: ✓ Upon completion of treatment or engraftment during treatment, whichever comes first ✓ Upon premature treatment discontinuation for any reason	
 ✓ At the end of monitoring or ext monitoring period ✓ In case of re-occurrence of malignant disease, GvHD diagnosis, uncontrolled infection or clinical manifestations of infections representing exclusion criteria at time of treatment ✓ If a second HSCT is required ✓ If any prohibited med is taken during the monitoring periods

Table 3 Transition between periods in case of ANC \geq 500 cells/ μ L during the monitoring period

Monitoring	Extended Monitoring	Treatment	Follow-up For emapalumab treated patients	Follow-up For non-emapalumab treated patients
As soon as ANC \geq 500 cells/ μ L during monitoring, enter extended monitoring	CXCL9 above threshold + Signs of sGF 	Enter treatment period	Enter follow-up period: ✓ Upon completion of treatment or engraftment during treatment, whichever comes first	Perform EoS visit and enter phone-calls follow-up period: ✓ At the end of monitoring or ext monitoring period ✓ In case of re-occurrence of malignant disease, GvHD diagnosis, uncontrolled infection or clinical manifestations of infections representing exclusion criteria at time of treatment
	If CXCL9 below threshold Continue extended monitoring unless a second HSCT is required		✓ Upon premature treatment discontinuation for any reason	
 ✓ If a second HSCT is required ✓ If any prohibited med is taken during the monitoring periods

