4.1 Inclusion criteria

1. Informed consent form signed by the patient (as required by law) or by the patient's legally authorized representative(s) with the assent of patients who are legally capable of providing it, as applicable.
2. Recipients of allogeneic HSCT and at high risk of GF, based on at least one of the following criteria:
 - Receiving reduced intensity conditioning (RIC) or non-myeloablative (NMA) conditioning, combined with a non-malignant disease or with a graft from Bone Marrow (BM).
 - *Ex vivo* T cell depleted graft.
 - Graft from mismatched unrelated or haploidentical donor.
 - Graft from Umbilical Cord Blood (UCB).
3. Patients requiring allo-HSCT with the following underlying diseases:
 - Malignant disease with high risk of GF, i.e. Acute Myeloid Leukemia (AML) and Acute Lymphoblastic Leukemia (ALL), with primary induction failure, second partial remission or relapse; Chronic Myeloid Leukemia (CML) in blastic phase (circulating blast or blast above 5% in biopsy); Non Hodgkin and Hodgkin Lymphoma and multiple myeloma with primary induction failure, second partial remission or relapse; myelodysplastic syndromes (MDS) and myeloproliferative disorders (MPD) with splenomegaly; myelofibrosis with portal hypertension pre-transplant; MDS/MPD overlap syndromes.
 - Non-malignant hematological diseases (e.g. autoimmune and metabolic disorders, aplastic anemia, Sickle cell anemia, Fanconi anemia, Diamond-Blackfan anemia, thalassemia, osteopetrosis, Wiskott-Aldrich syndrome, severe combined immunodeficiency, Hemophagocytic lymphohistiocytosis and other immunoregulatory disorders).
4. Male and female patients.
5. Children aged at least 1 year and adults. Once the appropriate dose has been determined in one of the three cohorts and safety has been assessed by the IDMC, children less than 1 year old may be included in the study.
6. Females of child-bearing potential, defined as all women physiologically capable of becoming pregnant, require the use of highly effective contraceptive measures from screening until 6 months after the last study drug administration.

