4.3 Criteria for women of childbearing potential

4.3.1 Acceptable methods of contraception

To ensure compliance, the study personnel must remind women of childbearing potential at each visit to use the methods of contraception defined for this study.

Females of child-bearing potential require the use of highly effective contraceptive measures (failure rate of less than 1% per year), from screening up to 6 months after the last study drug administration:

Highly effective contraceptive measures include:

- Sexual abstinence: refraining from heterosexual intercourse during the entire period defined above. The reliability of sexual abstinence needs to be evaluated in relation to its duration and compatibility with the preferred and usual lifestyle of the subject. Periodic abstinence (calendar, symptothermal, post-ovulation methods) is not an acceptable method of contraception.
- Hormonal contraceptives: combination or progesterone only.
- Intrauterine methods: intrauterine devices or systems.
- Bilateral tubal occlusion.
- Vasectomized partner.

The methods of birth control used (including non-pharmacological methods) must be recorded in the electronic Case Report Form (eCRF).

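### Mandatory pregnancy reporting stops at the EoS visit, about two weeks before the protocol's 6-month contraception period ends for treated patients

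*Combined protocol and SAP*

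**What the plan says.** - **Reporting period.** Section 9.3.1 states that "any pregnancy up to EoS visit must be reported", whether or not emapalumab was given. The next sentence, "All pregnancies should be reported using the Sobi Pregnancy Notification Form", goes on to set the recipient and a 24-hour limit.
- **Contraception period.** Inclusion criterion 6 (section 4.1) requires "contraceptive measures from screening until 6 months after the last study drug administration". Section 4.3.1 sets the same period: "from screening up to 6 months after the last study drug administration".
- **EoS visit, treated patients.** The protocol gives two windows. Section 3.4.5 first puts follow-up visit 6 at "24 weeks \pm 2 weeks after last study drug administration (EoS visit"); the synopsis and Tables 7a and 7b agree. Later in section 3.4.5, under the End of Study Visit, the same visit is placed "at week 24 \pm 2 days from last study drug administration", and the synopsis repeats that too.
- **EoS visit, untreated patients.** "Non-emapalumab treated patients will require to attend the EoS visit within 1 week from the last day in the monitoring periods". They have no drug exposure, so this point does not concern them.
- **After EoS.** Treated patients have phone calls at 1, 2 and 3 years after HSCT. These cover survival, GvHD, listed procedures and medications, and related SAEs. Pregnancy is not listed, and Table 7a schedules no pregnancy test after the FU6/EoS column. Under section 9.2.2 a new SAE is reportable at this stage only "if considered causally related to previous exposure to the study treatment by the investigator".

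**The concern.** The protocol takes pregnancy seriously. It excludes pregnant women, requires contraception, repeats pregnancy tests, stops treatment if pregnancy occurs, and has a notification form with outcome follow-up. One would expect the duty to report to last as long as the duty to prevent. For treated patients it does not: reporting is tied to a visit, contraception to a calendar period, and the visit normally comes first.

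At stake is a small piece of safety information. A site following 9.3.1 literally could learn of a pregnancy that began while contraception was still required and have no duty to send the form. Its outcome would then not be followed under section 9.3.2.

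**Working it through.** The plan states no figure for this interval, so there is none to reproduce. The check is date arithmetic.

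**Inputs**

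- End of contraception period: 6 calendar months after the last dose (sections 4.1 and 4.3.1). Over all start dates in a four-year cycle this is 181 to 184 days, mean 182.6.
- Nominal EoS visit: week 24, that is 24 × 7 = day 168 after the last dose.
- EoS window, version A: ± 2 weeks, day 154 to day 182.
- EoS window, version B: ± 2 days, day 166 to day 170.

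**Formula:** uncovered interval = (6 months in days) − (EoS day).

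| EoS day | Source | Shortest | Longest |
|---|---|---|---|
| 154 | A, earliest | 181 − 154 = 27 | 184 − 154 = 30 |
| 166 | B, earliest | 181 − 166 = 15 | 184 − 166 = 18 |
| 168 | nominal | 181 − 168 = 13 | 184 − 168 = 16 |
| 170 | B, latest | 181 − 170 = 11 | 184 − 170 = 14 |
| 182 | A, latest | 181 − 182 = −1 | 184 − 182 = 2 |

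Under A the interval runs from nil to 30 days. Under B it runs from 11 to 18 days and never closes.

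**Drug remaining, for materiality only.** Section 1.2.3.1 gives a half-life of around 22 days. Assuming simple linear decay, the fraction left after *t* days is 0.5^(*t*/22):

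- day 154: 0.5^7 = 0.8%
- day 168: 0.5^7.64 = 0.5%
- day 182.6: 0.5^8.3 = 0.3%

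That half-life comes from healthy adults. Section 5.3 says clearance rises with IFNγ production, so these fractions are only indicative.

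**Can the 1-year call carry the question?** Take the latest start of treatment as Day 98 + 3 = 101 after HSCT, with up to 56 days of treatment. The last dose then falls by day 101 + 56 = 157, and 6 months later is at most day 157 + 184 = 341. The nominal 1-year call is at about day 365, after that date. Its window is ± 4 weeks, so a call at the earliest day, 365 − 28 = 337, could precede day 341 by 4 days in the extreme case.

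**The case against.** Several arguments on the other side have force.

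- **Week 24 may be meant as 6 months.** That is plausible, and with the visit at week 26 the interval all but vanishes. It does vanish only at that edge of the wider window; at the nominal date about two weeks remain.
- **The instruction to report all pregnancies could be read without a time limit.** It follows directly on the sentence that sets the EoS limit, and it deals with form and timing. A site could reasonably stop at EoS.
- **Serious outcomes are still caught.** This stands. A congenital anomaly is an SAE under section 9.2.1, and a related SAE after EoS stays reportable under section 9.2.2. A reader might infer that these pregnancies are never reported; the documents support only that they need not be. What may be lost is notice of an uncomplicated pregnancy, or of an event judged unrelated.
- **The protocol defines no fetal risk window.** This stands too. A reader might infer that the 6 months are such a window, with material exposure throughout. The protocol sets only a contraception period, and on the decay assumption little drug remains by then.
- **The numbers are small.** At most 3 × 4 + 6 = 18 evaluable patients are planned for primary GF, plus non-evaluable patients and those optionally treated for secondary GF. Only women of childbearing potential among them matter here.

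A reader might also lengthen the interval by adding conceptions too recent to show on the urine test at EoS. With an assumed 14-day lag and the earliest visit day, that gives 28.6 + 14 = 42.6 of 182.6 days, about 6 of 26 weeks. The documents do not support this figure. They give no test lag, it stacks an assumption on the worst case, and a pregnancy conceived before EoS may already count as one up to EoS. What the text does show is that it leaves the question open.

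**Conclusion.** The mismatch is real and minor. For treated patients, mandatory pregnancy reporting ends before the stated contraception period does: by about 13 to 16 days at the nominal visit, 0 to 30 days if the window is ± 2 weeks, and 11 to 18 days if it is ± 2 days. Section 9.3.1 also does not say whether conception or detection decides, and the two EoS windows contradict each other.

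This rests on reading 6 months as calendar months and on the EoS limit in 9.3.1 governing the sentence after it. The effect is a possible loss of a few late notifications. No endpoint, sample size or analysis is touched.

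**What to change.** Reconcile section 9.3.1 with sections 4.1 and 4.3.1, so that for treated patients the reporting period matches the contraception period that the protocol itself states. In the same sentence, say whether the date of conception or of detection governs. State one EoS window for treated patients throughout the synopsis, section 3.4.5 and Tables 7a and 7b; which window is for the sponsor to settle.

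If reporting then extends past EoS, add a pregnancy question for treated women of childbearing potential to the existing 1-year call in Table 7a, asking about the whole period since the last visit. A call made early in its window should allow for the 4-day extreme case shown above.

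The cost is a short wording change and one extra question on a call already scheduled. No visit or test is added, and treatment and contraception requirements stay as they are.
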